11.3 Primary Breast Cancer Diagnosis

To describe the clinical profile of the patients, the below characteristics related to the primary breast cancer diagnosis will be presented for FAS and by subgroup EU label; Pathologic stage; Residual disease after neoadjuvant treatment; Risk profile; Previous adjuvant or neoadjuvant therapy and Prior trastuzumab-based regimen overall and last treatment (Section 8.4):

- Age at primary diagnosis of breast cancer, calculated as:
 - *Year of breast cancer diagnosis – Year of birth*
- Age at primary diagnosis of breast cancer category: < 40 years, 40 to 49 years, 50 to 59, 60 to 69, >=70
- HER2 overexpression/amplification testing:
 - Immunohistochemistry (IHC): Yes, No, Unknown
 - If IHC, the result obtained: IHC 3+ (positive), IHC 2+ (equivocal)
 - Fluorescence in situ hybridization (FISH): Yes, No, Unknown
 - If FISH, the result obtained: Positive, Equivocal
 - Chromogenic in situ hybridization (CISH): Yes, No, Unknown
 - If CISH, the result obtained: Amplified, Non-amplified
- HER2 overexpression/amplification testing combination of results: IHC and FISH, IHC and CISH

- Hormone receptor status: ER positive, PR positive, ER negative, and PR negative
 - If ER or PR positive: Receptor expression (%) score, Score unavailable
- Ki-67 protein levels category: Low, Medium, High, Unavailable
 - For each category: Ki-67 protein levels (%), Unavailable
- Primary tumor location: Left Breast, Right Breast
 - For each side the exact location: Upper-outer quadrant, Upper-inner quadrant, Lower-outer quadrant, Lower-inner quadrant, Nipple complex, Axillary tail, Other
- Sentinel lymph node biopsy performed: Yes, No, Unavailable
 - If yes: Positive, Negative
- Primary tumor histology: Infiltrating ductal carcinoma, Infiltrating lobular carcinoma, Invasive carcinoma, Tubular, Other
- Histological grade: G1 Well differentiated, G2 Moderately differentiated, G3 Poorly differentiated, G4 Undifferentiated, Unavailable
- Stage of Breast Cancer: TX, T0, T1, T2, T3, T4, Tis
 - If T1, specified category: T1a, T1b, T1c, Unavailable
 - If T2, specified category: T2a, T2b, Unavailable
- Regional Lymph Nodes (N): NX, N0, N1
- Number of lymph nodes involved: 0, 1-3, ≥ 4
- TNM stage: T0N1M0, T1N0M0...
- Pathologic stage (AJCC classification): I, IIA, IIB, IIIA, IIIB, IIIC

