4.3.1 Primary outcome

Demographics and clinical profile of patients with early-stage HER2+ breast cancer will be described, for the full analysis set and by subgroup(s) of interest, if the number of patients allow, (see section 4.3.4). The following baseline data will be collected at study entry:

1. Patient demographic and clinical characteristics at neratinib initiation, unless stated otherwise:
 - Age (year of birth), gender, weight, height, body mass index (BMI)
 - Performance status using the Eastern Cooperative Oncology Group (ECOG), Karnofsky or any other scoring system at primary diagnosis of breast cancer and at neratinib initiation
 - Employment status
 - Date of primary diagnosis of breast cancer
 - Menopausal status at primary diagnosis of breast cancer
 - Location of the primary tumor at primary diagnosis of breast cancer
 - Histology of primary diagnosis of breast cancer
 - Histological grade (Grade 1, Grade 2, Grade 3)
 - Histological subtype (Ductal, Lobular, Other etc.)
 - Breast Cancer stage at the time of primary diagnosis, using the Tumor/Node/Metastasis (TNM) classification system (I, II, III)¹⁹
 - Pathological Stage (American Joint Committee on Cancer classification) at the time of primary diagnosis
 - Relevant comorbidities at neratinib initiation, including, but not limited to the following:
 - Renal disease
 - Liver disease
 - Gastro-intestinal disorders
 - Cardiovascular conditions
 - Skin and subcutaneous tissue disorders
 - Diabetes (Type I or II)
 - Tumor biology
 - HR status (estrogen receptor [ER] and progesterone receptor [PgR] status)
 - HER2 overexpression/amplification
 - Ki-67 (if available)
 - Grading

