8.4 Examination of Subgroups

The following subgroups are of interest, based on patient characteristics at neratinib initiation (index date) or primary diagnosis of breast cancer. Analyses of primary, secondary, and exploratory outcomes may be performed for some or all these subgroups, subject to pertinence and the number of patients in each subgroup:

- EU label status: Yes, No
 - Yes, defined as, HR+ patients with initiation of Neratinib ≤ 1 year from trastuzumab-based treatment completion in adjuvant setting (EU Label population)
 - No, otherwise
- Pathologic stage (AJCC classification) at primary breast cancer: Stage I, Stage II+III
 - If missing, derived as in 2
- Residual disease after neoadjuvant treatment (pathologic complete response [pCR]): pCR, No pCR

- Risk: Low risk (Stage I or N- or pCR), High risk (Stage II/III or N+ or no pCR)
 - N-, defined as, the electronic case report form (eCRF) nodal status category of NX or N0
 - N+, defined as $N \geq 1$ nodal
- Previous adjuvant or neoadjuvant therapy ⁽²⁾: Neoadjuvant + Post neoadjuvant treatment, Adjuvant only
 - Neoadjuvant + Post neoadjuvant, defined as, at least one neoadjuvant and one adjuvant treatment
 - Adjuvant only, defined as, at least one adjuvant treatment and no neoadjuvant
- Prior trastuzumab-based regimen overall (neoadjuvant or adjuvant): Trastuzumab only, Trastuzumab and Pertuzumab, Trastuzumab emtansine (T-DM1), Other anti HER2
- Prior trastuzumab based regimen the last treatment in adjuvant setting before Neratinib initiation: Trastuzumab only, Trastuzumab and Pertuzumab, Trastuzumab emtansine (T-DM1), Other anti HER2
- Hormone Receptor at Primary Breast Cancer Diagnosis: HR+, HR-
 - HR+, defined as either ER or PR or both are positive
 - HR-, defined as if ER and PR are negative
- Concomitant Corrective Antidiarrheal: Yes, No
- Concomitant Prophylaxis Antidiarrheal: Yes, No
- Initial Dose of Neratinib: <240mg, 240mg, >240mg

Table 2 AJCC staging

Primary tumor (T)	Regional lymph nodes (N)	Distant metastasis (M)	Stage
Tis	N0	M0	0
T1	N0	M0	IA
T0	N1	M0	IB
T1	N1	M0	IB
T0	N1	M0	IIA
T1	N1	M0	IIA
T2	N0	M0	IIA
T2	N1	M0	IIB
T3	N0	M0	IIB
T0	N2	M0	IIIA
T1	N2	M0	IIIA
T2	N2	M0	IIIA
T3	N1	M0	IIIA
T3	N2	M0	IIIA
T4	N0	M0	IIIB
T4	N1	M0	IIIB
T4	N2	M0	IIIB
Any T	N3	M0	IIIC
Any T	Any N	M1	IV

N2 and N3 are not collected in the CRF, this regional lymph node categories will be identified by “ ≥ 4 ” lymph nodes involved.

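### The N row of SAP 11.3 stops at N1, although the SAP treats four or more involved nodes as N2 or N3; a stage derived for such patients has two answers (minor)

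*SAP*

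**What the plan says.** SAP 11.3 describes the primary diagnosis, which belongs to the primary outcome. Four of its rows matter here:

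- nodal category: "Regional Lymph Nodes (N): NX, N0, N1"
- node count: "Number of lymph nodes involved: 0, 1-3, ≥ 4"
- a combined TNM row, given by two examples and left open: "TNM stage: T0N1M0, T1N0M0"
- stage: "Pathologic stage (AJCC classification): I, IIA, IIB, IIIA, IIIB, IIIC"

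SAP 8.4 has a two-level stage subgroup, "Pathologic stage (AJCC classification) at primary breast cancer: Stage I, Stage II+III", with the rule "If missing, derived as in 2", which I read as Table 2 (AJCC staging). Table 2 has separate lines for N1, N2 and N3. The note beneath it reads "N2 and N3 are not collected in the CRF, this regional lymph node categories will be identified by" the category of four or more involved nodes.

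The recorded stage is a planned data item in its own right. Protocol 4.3.1 lists "Pathological Stage (American Joint Committee on Cancer classification) at the time of primary diagnosis".

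**The concern.** The N row and the Table 2 note disagree about the same patients. By the note, someone with four or more involved nodes is N2 or N3. In the N row the only node-positive value is N1. The next row of the same table would show that patient's node count as four or more, so the two rows would not agree.

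The note also lets one recorded value stand for two categories that Table 2 sends to different substages. Two programmers could both follow the SAP and derive different stages for the same patient.

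The study is purely descriptive, and its primary objective is the demographic and clinical profile. SAP 7.10 removes nodal status from the subgroups of interest, so the rows of 11.3 are where nodal burden is described. What is at stake is the correctness and reproducibility of a descriptive table. No test or effectiveness estimate depends on it.

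**Working it through.** The plan gives no figure to reproduce. The check is a lookup in SAP Table 2.

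**Inputs.** The T, N and stage lines come from SAP Table 2, all with M0. The node-count categories come from SAP 11.3. The note under Table 2 maps four or more nodes to N2 or N3. I take 0 nodes as N0 and 1-3 nodes as N1, the categories that remain once the note has assigned four or more.

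**Step 1: the N row.** The available values are NX, N0 and N1. A node-positive patient with a known category can only be N1, so a patient with four or more nodes is counted as N1. By the note the same patient is N2 or N3. This follows from the text alone.

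**Step 2: the TNM row.** The SAP does not say whether N in this row comes from the eCRF field or from the node count. If it comes from the field, a T2 patient with four or more nodes prints as T2N1M0. If it comes from the count, the patient cannot be printed as one string, because N2 and N3 are not separated.

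**Step 3: derived stage.** All stages that Table 2 allows:

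| T | 1-3 nodes (N1) | 4 or more nodes (N2 or N3) |
|---|---|---|
| T0 | IB or IIA | IIIA or IIIC |
| T1 | IB or IIA | IIIA or IIIC |
| T2 | IIB | IIIA or IIIC |
| T3 | IIIA | IIIA or IIIC |
| T4 | IIIB | IIIB or IIIC |

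All five cells in the right-hand column have two answers, and IIIC can never be assigned uniquely. T3 with 1-3 nodes is IIIA without ambiguity. The double entry for T0 and T1 with N1 is a separate defect of Table 2, since those combinations are listed under both IB and IIA. It does cross the Stage I boundary, but it has nothing to do with the upper end of the N field.

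**Step 4: documented uses of derived stage and N.**

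- Stage I versus Stage II+III: every cell in the right-hand column is Stage III, so the group is the same under N2 and N3. This holds provided the note is applied. If the count were ignored and the field value N1 used, the N1 column would apply, and T0 and T1 would no longer be clearly outside Stage I. The note is there to prevent that.
- Risk subgroup: N+ means N of 1 or more, so N1, N2 and N3 are pooled.
- The I to IIIC row of 11.3: the SAP does not say whether derived stages enter it. The IIIA/IIIC or IIIB/IIIC ambiguity would become visible there only if they do.

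**The case against.** The strongest reply is that nothing is lost. The node count has its own row directly below the row listing the involved nodes by category, so high nodal burden is shown openly, and the SAP states plainly that N2 and N3 were not collected. Derivation applies only when the recorded stage is missing. The rule for it sits under a two-level subgroup that the ambiguity cannot change, and SAP 8.3 says missing data are generally not imputed. Output format and content are left to the table shells (SAP 9), which are not among the documents. Most of this stands, and it is why the point is minor. It does not repair the N row, whose listed categories conflict with the SAP's own note.

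A reader might infer three stronger things that the documents do not support:

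- **That the TNM row certainly prints these patients as N1.** The row is an open list with no stated source for N, so this is conditional on the eCRF field being used.
- **That a derived Stage IIIA can never be told from IIIC.** This is true for T0 to T3 with four or more nodes, but not for T3 with 1-3 nodes. For T4 the confusion is between IIIB and IIIC.
- **That the number of patients can be estimated.** Assuming that 15-25% of the 120 patients in SAP 4.2 have four or more nodes gives 0.15 × 120 = 18 to 0.25 × 120 = 30. Nothing in the documents supports that share. Even then it would count only the N label. The substage problem needs four or more nodes and a missing recorded stage together, and neither count is given.

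**Conclusion.** The N row of SAP 11.3 is wrong as written: it counts patients with four or more involved nodes as N1 (unless NX), while the Table 2 note makes them N2 or N3. The TNM row has the same fault if it uses the eCRF N field, which the SAP leaves open. Separately, the Table 2 derivation gives two substages for all five T categories with four or more nodes: IIIA or IIIC for T0 to T3, and IIIB or IIIC for T4. That second part matters only for patients whose recorded stage is missing, and only if derived stages are shown by substage.

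With the note applied, the Stage I versus II+III split is unaffected, and the risk subgroup does not separate N1 from N2 or N3. The number of patients concerned cannot be derived from the documents. The point is a minor correction to a primary-outcome table and changes no inferential result.

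**What to change.** In SAP 11.3, report N as NX, N0, N1 (1-3 nodes) and N2-N3 (four or more nodes), using the node count already collected. State that the TNM string is built from this variable. Say in 8.4 or 11.3 whether derived stages enter the I to IIIC row. If they do, label cases with four or more nodes as Stage III, substage not determinable, and do not assign IIIA, IIIB or IIIC.

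The cost is a few lines of SAP wording and one derivation, with no new data. The downside is that derived substages are merged within Stage III; the change cannot recover the N2/N3 distinction, which was not collected. If the database is already locked, Protocol 4.7.1 provides for describing the change in the study report or statistical analysis report.

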12 SECONDARY OUTCOMES

12.1 Neratinib Treatment Patterns

Neratinib treatment patterns will be described as frequencies and percentages or summary statistics, as appropriate, for FAS and by subgroup EU label; Pathologic stage; Residual disease after neoadjuvant treatment; Risk profile; Previous adjuvant or neoadjuvant therapy and Prior transtuzumab-based regimen overall and last treatment (Section 8.4).

For duration of neratinib treatment calculations, the date of first and last neratinib administration will be taken from the eCRF “Neratinib Treatment” form, variables “Neratinib Initiation date” and “Definitive discontinuation date” respectively. Interruptions, compliance, and dose changes are not considered for duration of neratinib treatment.

Neratinib treatment initiation details:

- Time from breast cancer diagnosis to neratinib initiation (months), calculated as:
 - $(Date\ of\ first\ neratinib\ administration - Date\ of\ diagnosis + 1) / 30.4$
- Time from completion of adjuvant trastuzumab-based therapy to neratinib initiation (months), calculated as:
 - $(Date\ of\ first\ neratinib\ administration - Date\ of\ completion\ of\ adjuvant\ trastuzumab-based\ therapy + 1) / 30.4$
- Performance status scale used at neratinib initiation: ECOG, Karnofsky, Other
 - If ECOG: 0, 1, 2, 3, 4, Unavailable
 - If Karnofsky: 100, 90, 80, 70, 60, 50, 40, 30, 20, 10, Unavailable and 90-100, 70-80, 50-60, 30-40, 10-20, Unavailable
- Performance status computed ECOG score (based on Table 3): 0, 1, 2, 3, 4, Unavailable
- Duration of neratinib treatment (months), calculated as:
 - For discontinued treatment,
 $(Date\ of\ last\ administration - Date\ of\ first\ administration + 1) / 30.4$

Document: ZZA65950_NEAR_SAP_v2.0

Author: [name]

Version Number: 2.0

Version Date: 22SEP2023

- For ongoing treatment, (*EOB date - Start date + 1*)
- Duration of neratinib treatment (categorized): ≤ 3 months, > 3 months to < 12 months, 12 months, >12 months
- Initial daily dosage (mg)
- Initial daily dose (mg), category: 40mg, 80mg, 120mg, 160mg, 200mg, 240mg, ...; and <240mg, 240mg, >240mg

Treatment modifications (dosage changes):

- Number and percentage of patients with at least one neratinib treatment modification. Percentage computed among FAS.
- Number of temporary modifications by patient
- Temporary modifications per patient category: 1, 2, >2. Percentage computed among FAS patients with at least one neratinib treatment modification.
- Number and percentage of patients by reasons reported for all treatment modifications: Worsening condition, Adverse event, Physician's decision, Patient's wish, Other. All dose changes will be captured in the CRF, therefore a patient can contribute to several reasons. Percentage computed among FAS patients with at least one neratinib treatment modification.
- Number and percentage of patients by reason for first treatment modification: Worsening condition, Adverse event, Physician's decision, Patient's wish, Other. All dose changes will be captured in the CRF, therefore a patient can contribute to several reasons.
- Number and percentage of patients by reason for subsequent treatment modifications⁽¹⁾: Worsening condition, Adverse event, Physician's decision, Patient's wish, Other. All dose changes will be captured in the CRF, therefore a patient can contribute to several reasons.
- Dose at first modification (mg)

- Dose at first modification (mg), category: 40mg, 80mg, 120mg, 160mg, 200mg, 240mg; and <240mg, 240mg, >240mg. Percentage computed among FAS patients with at least one neratinib treatment modification.
- Dose at subsequent modifications (mg)⁽¹⁾
- Dose at subsequent modifications (mg)⁽¹⁾, category: 40mg, 80mg, 120mg, 160mg, 200mg, 240mg; and <240mg, 240mg, >240mg. Percentage computed among FAS patients with the subsequent neratinib treatment modification.

⁽¹⁾Presented individually for each modification.

- Dose reduction at first modification: Yes, No. Percentage calculated among patients with at least one neratinib treatment modification.
 - Dose reduction⁽²⁾
 - Dose reduction⁽²⁾ category: 1 tablet, 2 tablets, > 2 tablets. Percentage calculated among patients with a reduction at first modification.
- Dose escalation at first modification*: Yes, No. Percentage calculated among patients with at least one neratinib treatment modification.
 - Dose escalation⁽²⁾
 - Dose escalation⁽²⁾ category: 1 tablet, 2 tablets, > 2 tablets. Percentage calculated among patients with an escalation at first modification.

⁽²⁾ 1 tablet of neratinib corresponds to 40 mg.

Temporary neratinib treatment discontinuations details:

- Number and percentage of patients with at least one temporary treatment discontinuation. Percentage computed among FAS.
- Number of temporary discontinuations by patient
- Temporary discontinuations per patient category: 1, 2, >2

- Number and percentage of patients by reason for all temporary discontinuations: Worsening condition, Adverse event, Physician's decision, Patient's wish, Other. All temporary discontinuations will be captured in the CRF, therefore a patient can contribute to several reasons. If the same reason was reported several times for the same patient, the patient contributes only once to the reason. Percentage computed among FAS patients with at least one temporary neratinib treatment discontinuation.
- Number and percentage of patients by reason for first temporary discontinuation: Worsening condition, Adverse event, Physician's decision, Patient's wish, Other. All temporary discontinuations will be captured in the CRF, therefore a patient can contribute to several reasons. Percentage computed among FAS patients with at least one temporary neratinib treatment discontinuation.
- Number and percentage of patients by reason for subsequent temporary discontinuations⁽¹⁾: Worsening condition, Adverse event, Physician's decision, Patient's wish, Other. All temporary discontinuations will be captured in the CRF, therefore a patient can contribute to several reasons. Percentage computed among FAS patients with at least one temporary neratinib treatment discontinuation.
- Dose at first re-initiation (mg)
- Dose at first re-initiation (mg), category: 40mg, 80mg, 120mg, 160mg, 200mg, 240mg; and <240mg, 240mg, >240mg
- Dose at subsequent re-initiations (mg)⁽¹⁾
- Dose at subsequent re-initiations (mg)⁽¹⁾, category: 40mg, 80mg, 120mg, 160mg, 200mg, 240mg; and <240mg, 240mg, >240mg

⁽¹⁾Presented individually for each re-initiation.

- Duration of first treatment interruption (days), calculated as:
 - $(End\ date\ of\ the\ first\ neratinib\ treatment - Start\ date\ of\ first\ re-initiation + 1)$

- Duration of subsequent treatment interruptions (days)⁽²⁾, calculated as:
 - *(End date of the previous neratinib treatment – Start date of subsequent re-initiation + 1)*

⁽²⁾Presented individually for each treatment interruption.

Permanent neratinib treatment discontinuation:

- Number and percentage of patients who discontinued the treatment permanently. Percentage computed among FAS.
- Number and percentage of patients by duration of treatment before discontinuation: ≤ 3 months, > 3 months to < 12 months, 12 months and > 12 months. Percentage computed among FAS patients who discontinued neratinib treatment permanently.
- Number and percentage of patients by reason for definitive discontinuation: Disease recurrence, Adverse event, Patient's wish, Physician's decision, Patient death, End of treatment period, Other. Percentage computed among FAS patients who discontinued neratinib treatment permanently.
 - Number and percentage of patients by switch onto another treatment following definitive discontinuation: Yes, No. Percentage computed among FAS patients who discontinued neratinib treatment permanently.

To supplement descriptions of neratinib treatment patterns for FAS, the Kaplan-Meier and reverse Kaplan Meier methods will be used. For Kaplan Meier, the number of events, number of censored data, median survival estimates will be reported along with the 1st and 3rd quartiles, and the corresponding two-sided 95% CI. Estimates of the proportion of patients not presenting the event of interest at 3-month intervals (1, 3, 6, 9, 12, 15, 18 months) and the corresponding two-sided 95% CIs. For the reverse Kaplan Meier, the number of events, number of censored data points, median follow-up time, Q1 and Q3 follow-up time and corresponding two-sided 95% CI will be presented. Kaplan Meier and reverse Kaplan Meier methods will be used for the following outcomes:

Document: ZZA65950_NEAR_SAP_v2.0

Author: [name]

Version Number: 2.0

Version Date: 22SEP2023

- Time from neratinib initiation to first temporary discontinuation (treatment persistence)
- Time from neratinib initiation to permanent treatment discontinuation⁽¹⁾
- Time from neratinib initiation to first treatment modification

⁽¹⁾ For the analysis of time to permanent discontinuation, death will be considered as an event.

Additionally, the Kaplan-Meier and reverse Kaplan Meier analysis will also be performed for permanent treatment discontinuation by subgroups Concomitant Prophylaxis Antidiarrheal and Initial Dose of Neratinib (section 8.4).

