Neratinib (Nerlynx®), an orally available, irreversible tyrosine kinase inhibitor (TKI), was approved by the Food and Drug Administration (FDA) in 2017 and in the European Union (EU) in 2018. In the EU, Neratinib's approved indication is for extended adjuvant therapy of adult patients with early-stage Hormone Receptor-positive (HR+) HER2-overexpressed/amplified breast cancer and who completed prior adjuvant trastuzumab-based therapy less than one year ago. The recommended dose of neratinib is 240 mg (six 40 mg tablets) taken orally once daily, continuously for one year¹⁵. Comparatively, the FDA approved indication applies to a broader profile of patients, where neratinib as a single agent is approved for the extended adjuvant

 Pierre Fabre TEMP CQA 0092 V2.0 Owning site : CORPORATE QA	Template to use for writing Corporate document, except Corporate policy and form, WORD in english	Page 10/29
--	--	------------

therapy of adult patients with early-stage HER2-positive breast cancer, to follow adjuvant trastuzumab-based therapy. Nothing is specified in terms of HR status or the length of prior adjuvant trastuzumab-based therapy.

Certain patients may have received neratinib as per the FDA indication, as part of the EAP in Europe.

Results of the ExteNET trial showed that patients with early-stage HER2+ breast cancer receiving one year of extended adjuvant therapy with oral neratinib (within a year of standard of care adjuvant trastuzumab), had significant improvement in the 2-year iDFS rate compared to placebo (93.9% versus 91.3%, respectively; hazard ratio, 0.67; 95% Confidence Interval (CI), 0.50–0.91; $p = 0.0017$)¹⁶. A 5-year follow-up reported similar results (hazard ratio 0.73; 95% CI 0.57–0.92; $p=0.008$)¹⁷. Furthermore, greater improvement in iDFS was observed in HER2+ patients with HR+ breast cancer¹⁶⁻¹⁸.

An Early access program (EAP) was initiated in Europe in 2017, providing access to neratinib to individual patients following specific criteria outside of a clinical trial. This program is currently ongoing in certain European countries, awaiting product reimbursement. This study will provide real-world data to characterize the profile of patients treated with neratinib, their previous medical history, the conditions for using neratinib and its profile in terms of safety and effectiveness as an extended adjuvant therapy. The profile of patients may be more diverse compared to those enrolled in the ExteNET trial.

Rationale

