4.2 Sample Size

Sample size calculation is not applicable, since the study plans to include all eligible breast cancer patients having received neratinib as an extended adjuvant therapy through the EAP in the target European countries. The number of patients is estimated to be up to 200 patients. Using the table below, the precision estimates for a 95% confidence interval (CI) were calculated around proportions ranging from 10% to 50% for a sample size between 150 and 300 patients (see Table 1).

A sample size of 200 patients would allow to assess a category of primary objective (demographic and clinical description of eligible patients) of 10%, 20%, 30%, 40% and 50% of patients with a precision of approximately $\pm 4.1\%$, $\pm 5.5\%$, $\pm 6.4\%$, $\pm 6.8\%$ and $\pm 6.9\%$, respectively.

Based on the feasibility, 120 patients would be enrolled instead of 200 patients originally planned.

A sample size of 120 or 100 patients would allow to assess a category of primary objective (demographic and clinical description of eligible patients) of 10%, 20%, 30%, 40% and 50% of patients with a precision of approximately $\pm 5.4\%$ or 5.9% , $\pm 7.2\%$ or 7.9% , $\pm 8.2\%$ or 9% , $\pm 8.8\%$ or 9.6% and $\pm 9\%$ or 9.8% , respectively.

Table 1 Precision estimates for 95% CI around proportions

Precision estimate*	Proportion				
	10%	20%	30%	40%	50%
Sample size	10%	20%	30%	40%	50%
100 patients	5.9%	7.9%	9%	9.6%	9.8%
120 patients	5.4%	7.2%	8.2%	8.8%	9%
150 patients	4.8%	6.4%	7.3%	7.8%	8.0%
200 patients	4.1%	5.5%	6.4%	6.8%	6.9%
250 patients	3.7%	4.9%	5.7%	6.1%	6.2%
300 patients	3.4%	4.5%	5.2%	5.5%	5.6%

*Precision estimates for a 95% CI were calculated using statistical analysis system (SAS) version 9.4 or higher (SAS Institute, Cary, NC, USA)

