7 GENERAL CONSIDERATIONS

7.1 Patient Identification Period

The patient identification period is the eligibility time window for selection of patients who initiated neratinib treatment within the EAP in Europe between 01 August 2017 and 31 December 2020.

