7.5 Study Entry Date

The study entry date is defined as the cut-off date until when the eligible patients' data as obtained from medical charts are abstracted for analysis in the study. This date will be the same for all patients and corresponds to the date of first patient in, 05 July 2022.

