7.8 End of Observation (EOB) Date

The end of observation (EOB) date is defined as the study entry date, date of death or date of last contact, whichever happens first.

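### SAP 12.1 tabulates neratinib durations cut short by loss to follow-up as completed durations, and its formula for ongoing treatment omits the conversion to months

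*SAP*

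**What the plan says.** SAP 12.1 (Neratinib Treatment Patterns) has a single variable for duration of neratinib treatment, headed as being in months. For discontinued patients it is last minus first administration plus one day, divided by 30.4. The other branch reads "For ongoing treatment, (*EOB date - Start date + 1", and no division follows. The variable is then grouped: "Duration of neratinib treatment (categorized): ≤ 3 months, > 3 months to < 12 months, 12 months, >12 months". Nothing separates the two kinds of patient. The section applies to the full analysis set (FAS) and to subgroups by EU label, stage, residual disease, risk, previous therapy and prior trastuzumab-based regimen.

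SAP 7.8 states: "The end of observation (EOB) date is defined as the study entry date, date of death or date of last contact, whichever happens first". The study entry date is fixed in SAP 7.5: "This date will be the same for all patients and corresponds to the date of first patient in, 05 July 2022". SAP 7.1 covers "patients who initiated neratinib treatment within the EAP in Europe between 01 August 2017 and 31 December 2020". The Protocol's background section describes the course as "taken orally once daily, continuously for one year".

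Three related outputs are planned in SAP 12.1: the percentage of FAS patients who stopped permanently; a table with the same four categories restricted to those patients; and Kaplan-Meier estimates of time to permanent discontinuation, for FAS and by antidiarrheal prophylaxis and initial dose.

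**The concern.** For a patient with no recorded stop, the time from start to last contact is a lower limit on her duration. SAP 12.1 uses it as the duration itself, next to completed courses. Treatment duration is a named secondary objective, and the share under 12 months will be read as the share who did not complete the one-year course. That reading would be distorted by however many patients were lost on drug, and more so in subgroups with more loss.

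The missing divisor is a second fault in the same rule. A value in days sorted into categories defined in months puts almost every such patient in the wrong group, and mixes units in the mean, median and quartiles.

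**Working it through.** **1. The plan's own precision figure.** SAP 4.2 says "Based on the feasibility, 120 patients would be enrolled instead of 200 patients originally planned" and gives ±8.2% for a proportion of 30% at that size. Check: 1.96 × √(0.30 × 0.70 / 120) = 8.20 points. It reproduces.

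**2. Who can be misplaced.** From the latest index date, 31 December 2020, to the cut-off, 05 July 2022, is 551 days. By the SAP's convention, (551 + 1) / 30.4 = 18.2 months. Anyone truly on drug at the cut-off belongs above 12 months. Death on drug is a listed reason for definitive discontinuation, so it can be recorded as a stop. What remains below 12 months is essentially the patient whose last contact came before month 12 with no stop recorded.

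**3. The formula as printed.** A patient lost at 1 month has the value 30 and one lost at 5 months has 152. Both exceed 12. Only a patient lost within 12 days would avoid the top category. In the mean, six patients lost at about 6 months (182 days) contribute 6 × 182 / 120 = 9.1, where in months they would contribute 6 × 5.99 / 120 = 0.3.

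**4. The formula in months.** The same patients have the values 0.99 and 5.0 and fall in the short categories. SAP 12.2 divides ongoing durations by 30.4 where months are reported, and the 12.1 heading says months, so an omission is likely. SAP 13.1 has the same gap.

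**5. Size.** Assumptions: N = 120; L patients lost on drug before 12 months; 30% of the other N − L stopped before 12 months (A, rounded to whole patients). The documents give neither L nor the 30%.

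- Printed formula: A / N.
- In months: (A + L) / N.
- Expected truth if loss is independent of stopping: (A + qL) / N. Here q is the chance that a lost patient stops before month 12. With a constant stopping hazard and losses spread evenly over 12 months, q = 0.16.

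| L (share of N) | A | Printed formula | Expected truth | In months |
|---|---|---|---|---|
| 0 | 36 | 30.0% | 30.0% | 30.0% |
| 2 (2%) | 35 | 29.2% | 29.4% | 30.8% |
| 6 (5%) | 34 | 28.3% | 29.1% | 33.3% |
| 12 (10%) | 32 | 26.7% | 28.3% | 36.7% |

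At 10% loss the gap to the expected truth is 36.7 − 28.3 = 8.4 points in months, about the planned half-width, and 26.7 − 28.3 = −1.6 points as printed. With an assumed 20% stopping early, 5% and 10% loss give 24.2% and 28.3% in months against 19.7% and 19.4% expected. With 40%, they give 43.3% and 45.8% against 39.4% and 38.0%.

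Whatever the loss mechanism, the true share lies between A / N (no lost patient stopped before month 12) and (A + L) / N (all did).

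**The case against.** The strongest reply is that time on drug while observed is a legitimate exposure summary in a purely descriptive study, and that SAP 12.1 already supplies the rest. The discontinued-only table exists. The percentage permanently discontinued uses the FAS as denominator, so it counts the lost patients. A reader could subtract one table from the other, and Kaplan-Meier is planned. Much of this stands, and a reader who inferred that the pooled table is the only output covering these patients would be wrong. But subtraction leaves the reader to repair the table. The discontinued-only table omits the lost patients. The Kaplan-Meier analysis is not planned for the subgroups in which the pooled table is shown.

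A reader might also infer that the under-12-month share is simply inflated. The documents do not support that. Taken literally, the printed formula lowers the share. No rate of loss while on treatment is given; Protocol 4.10 speaks of attrition over the whole study, and with no such loss there is no error. If patients tended to stop drug at about the time of last contact, the months reading would be close to right and censoring them would overstate time on treatment. Nothing in the documents settles whether loss and stopping are independent.

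**Conclusion.** The point holds as a defect in a stated rule. Incomplete and completed durations share one summary, so patients lost on neratinib before 12 months are misclassified. The under-12-month share is a lower bound as printed (apart from losses within 12 days) and an upper bound if months are intended. On the months reading, with 120 patients and an assumed 30% stopping early among those with a known stop, the share moves from 30% with no loss to about 31%, 33% and 37% at 2%, 5% and 10% on-treatment loss. The excess over the expected truth is minor at the low end and about as large as the planned 8.2-point half-width at the high end. These sizes rest on an assumed loss rate, and the benchmark on loss being independent of stopping. A secondary outcome is affected; the primary outcome is not.

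**What to change.** In SAP 12.1:

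- Divide the ongoing branch by 30.4.
- Keep the completed-duration summary and categories for patients with a definitive discontinuation date, as the discontinued-only table already does.
- Report patients without that date in a separate row with time observed, split into last contact before the cut-off and ongoing at the cut-off.
- Extend the Kaplan-Meier analysis of time to permanent discontinuation to the subgroups listed in 12.1, where numbers allow, and state that these patients are censored at EOB. Section 12.1 gives no censoring rule of its own. Take the shares still on neratinib from these curves.
- Give the 12-month category a rounding rule or window. Twelve months is 364.8 days, so 364 days is 11.97 and 365 days is 12.01, and no whole number of days meets it exactly.

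No new data are needed. The cost is SAP wording, one table row and some further runs of a method already specified. The downside is slightly more output and imprecise curves in small subgroups.
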